each Institution's standards of care. In the PJ Group, the amylase value of drain fluids will be checked on POD1, POD3 and at any POD if it will help to diagnose a still undiscovered POPF. Surgical drain will be managed according to clinical judgment and each Institution's clinical standards. During hospitalization, all patients will receive specialistic evaluation to assess and possibly treat the occurrence of new onset diabetes or the worsening of pre-existing diabetes. Pancreatic exocrine insufficiency will be treated with oral supplementation of pancreatic enzymes if needed. Patients in the TP Group will be vaccinated 1 month after complete functional recovery against Pneumococcus, Hemophilus influenzae group B, and Meningococcus to minimize the likelihood of developing post-splenectomy sepsis. All patients will receive an outpatient follow-up, 1 month after discharge and every 6 months for 2 years. During follow-up, glycemic control, nutritional status, and possible symptoms of exocrine insufficiency will be assessed, and patients will receive specialistic assistance if needed. QoL will be registered using specific questionnaires. An oncologic evaluation will determine the indication for administration of adjuvant therapy, in case of malignancy.

Questionnaires

All patients who will be alive after at least 12 months of follow-up will be enrolled in the cross-sectional study of quality of life. All the eligible patients who are not able to attend outpatient visits will be contacted by telephone before receiving the 5 questionnaires by mail. Patients who will not respond within 1 month will be contacted again by telephone. Four questionnaires will be administered: (1) the EuroQoL Group questionnaire (EQ-5D); (2) the European Organization for Research and Treatment of Cancer (EORTC) QLQ-C30 questionnaire; (3) the European Organization for Research and Treatment of Cancer (EORTC) QLQ-PAN26 questionnaire; and (4) the Problem Areas in Diabetes (PAID) questionnaire.^{17 18 19 20} The comprehensive assessment will consist of a total of 116 questions.

ENDPOINTS

Primary endpoint

For each study group the primary endpoint is the rate of postoperative major morbidity, defined as Clavien-Dindo ≥ 3 .

Secondary endpoints

For each study group secondary endpoints are:

- Incidence of In-hospital, 30-days and 90-days postoperative mortality. Beyond these time-limits, the mortality that may be related to the operation will be considered and discussed in each case.

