- Incidence, severity, and overall average complication burden for PPH and DGE
- Incidence of other postoperative morbidity (see below)
- Time-to-functional recovery (functional recovery is defined by all of the following criteria: adequate pain control with only oral analgesia (no intravenous or epidural analgesia necessary); independent mobility; ability to maintain more than 50% of the daily required caloric intake; no need for intravenous fluid administration; and no signs of infection)²¹
- Length of hospital stay
- Postoperative endocrine insufficiency (new onset diabetes, worsening of pre-existent diabetes, insulin dependency). The definition of postoperative new onset of diabetes will be based on the reporting of a normal preoperative FBG/HbA1c and postoperatively by measured glucose metabolism including FBG/HbA1c level and/or insulin medication.
- Postoperative exocrine insufficiency (incidence of diarrhea, prescription of pancreatic enzymes, number of capsules). The definition of postoperative exocrine insufficiency will be based on FE-1

determination, the presence of steatorrhea and necessity of enzyme treatment with cessation/mitigation of diarrhea after enzyme supplementation.

- Access to adjuvant chemotherapy (when indicated)
- Delay in starting adjuvant chemotherapy, calculated as the time between surgery and the beginning of adjuvant chemotherapy (when indicated)
- General, cancer-specific, pancreas-specific and diabetes-related QoL (EQ-5D; EORTC QLQ C30 and PAN26; PAID) ^{17 18 19 20}

The observation period for postoperative morbidity will last until the complete recovery from surgery.

Morbidity will include:

- PPH as defined by ISGPS ²²
- DGE as defined by ISGPS ²³
- Bile leakage as defined by ISGLS²⁴
- Enteric fistula defined as presence of enteric fluid from drains, possibly confirmed by sinogram or plain radiography with oral contrast study
- Abdominal fluid collection defined as any intraabdominal fluid collections larger than 5cm confirmed at imaging
- Abdominal abscess defined as an intraabdominal fluid collection containing gas bubbles and producing clinically relevant signs of infection
- Wound infection as defined by CDC ²⁵
- Blood transfusions defined as the number of packed red blood cells unit transfused after the procedure
- Sepsis ²⁶
- Chyle leak as defined by ISGPS ²⁷
- Gastric venous congestion ¹⁶
- Postoperative liver failure
- Myocardial infarction
- Acute kidney injury
- Pulmonary embolism
- Pneumonia

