Continuous variables will be expressed as the means and standard deviation values or as median values with ranges and will be compared using the Student t-test or the Mann-Whitney test as appropriate. Categorical variables will be analyzed by Chi-square or Fisher's exact test in case of expected small frequencies. All the tests will be 2-tailed. P values < 0.05 will be considered statistically significant. All endpoints will require the above-mentioned statistical analysis, comparing the two study arms. Statistical analyses will be performed using STATA14 for Windows.

DURATION AND END OF THE STUDY

Since the Department of General and Pancreatic Surgery performs about 250 PD per year and the study will be proposed to at least other 2 international referral centers, the primary endpoint will be reached after 25 months: 22 months of patients' enrollment and 3 months of follow-up. Long term analysis of QoL and pancreatic insufficiency will require additional 24 month of follow-up. Time for data analysis must be considered negligible. All the patients undergoing PD will be enrolled for the study if inclusion and exclusion criteria will be respected. The study will be discontinued in case of reaching the statistical significance of the primary endpoint, or in case of suspension by the coordinators or by the authorities.

PROCEDURES RELATED TO REGISTRATION AND DATA MANAGEMENT

To ensure the confidentiality of data, each patient will be registered and de-identified by an identification code.

Each subject will be identified by a code consisting of:

- Code Protocol: TETRIS
- Number of the institution: (e.g. Patient recruited at the Verona Pancreas Institute will be coded as TETRIS_C1)
- Number of recruitment (e.g. the third patient recruited at the Verona Pancreas Institute will be coded as TETRIS_C1_3).

The P.I. of the study will be responsible for data protection and privacy of study participants by treating the data solely for statistical purposes and scientific research, and he will not communicate them if not anonymously. The manager of data processing is the principal investigator.

All data of enrolled patients collected during the study will be recorded in a computerized case report form (CRF) and transferred automatically into a specific database protected by passwords. These data will be kept confidential and will be treated in full compliance with the Legislative Decree 196/03.

ETHICAL CONSIDERATIONS

[figure not shown]

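### About 44 secondary comparisons are each tested at two-sided P < 0.05 and may be declared significant, with nothing limiting secondary claims and no between-arm estimate with an interval

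*Combined protocol and SAP*

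**What the plan says.** The Statistical Analysis section prescribes t-tests or Mann-Whitney tests for continuous variables. For the rest, "Categorical variables will be analyzed by Chi-square or Fisher's exact test in case of expected small frequencies". It continues: "All the tests will be 2-tailed", "P values < 0.05 will be considered statistically significant", and "All endpoints will require the above-mentioned statistical analysis, comparing the two study arms".

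The Endpoints section names a single primary endpoint: "the primary endpoint is the rate of postoperative major morbidity, defined as Clavien-Dindo ≥ 3". The secondary list is long. It opens with "Incidence of In-hospital, 30-days and 90-days postoperative mortality" and "Incidence, severity, and overall average complication burden for PPH and DGE". It goes on to an itemised morbidity list, recovery and length of stay, endocrine and exocrine insufficiency, adjuvant chemotherapy and four quality-of-life questionnaires.

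The Sample Size Calculation ties the 5% alpha and 80% power to one comparison, 40% versus 15% on Clavien-Dindo ≥ 3. No section gives a testing hierarchy, a key secondary endpoint, a multiplicity adjustment or an exploratory label for the secondary endpoints. None asks for a between-arm difference with a confidence interval.

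**The concern.** Followed as written, the rule attaches the same label to a chance difference in one listed complication as to the primary result. In a trial of 98 patients with dozens of comparisons, some of those labels may be false, and the report would have no stated basis for treating them with more caution.

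A separate problem runs the other way. The plan's output is a summary per arm plus a P value. For rare outcomes a non-significant P says little, but it is easily taken as equivalence. The background section already does this: it describes mortality of 3% versus 4% (p = 0.6) in the earlier retrospective series as comparable. Mortality is one of the outcomes on which total pancreatectomy and anastomosis have to be weighed, so the width of the uncertainty needs to be visible.

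**Working it through.** **1. The plan's own figure.** With p₁ = 0.40, p₂ = 0.15 and mean 0.275:

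n = [1.960·√(2·0.275·0.725) + 0.842·√(0.40·0.60 + 0.15·0.85)]² / 0.25² = (1.238 + 0.510)² / 0.0625 ≈ 48.9, so 49 per group (power 80.1%). The stated size reproduces, for the primary comparison only.

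**2. Count of between-arm secondary comparisons (Endpoints section).**

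| Group | Number |
|---|---|
| Mortality, three time windows | 3 |
| PPH and DGE: incidence, severity, burden | 6 |
| Other listed morbidity items | 18 |
| Re-admission, three windows | 3 |
| Functional recovery; length of stay | 2 |
| Endocrine insufficiency | 3 |
| Exocrine insufficiency | 3 |
| Chemotherapy access; delay | 2 |
| Quality of life, one score per questionnaire | 4 |
| **Total** | **44** |

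The endpoints defined for the PA group only are left out. Testing questionnaire subscales would raise the count.

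**3. Upper range.** All 44 nulls true, each test at full 5% size:
- Expected false positives: 44 × 0.05 = 2.2.
- Independent: 1 − 0.95⁴⁴ = 0.895.
- Common correlation between test statistics (assumed; simulated): 77% at 0.3, 59% at 0.5, 39% at 0.7.

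**4. Two corrections that lower it.**

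*Endpoints where a real difference is expected.* The background section reports, for the earlier series, differences in PPH, DGE, fluid collection, length of stay and sepsis, and worse diabetes-specific quality of life and universal insulin-dependent diabetes after TP. Exocrine insufficiency is also expected to differ after removal of the whole gland. Removing these: 44 − 6 (endocrine/exocrine) − 6 (PPH/DGE) − 1 (fluid collection) − 1 (sepsis) − 1 (length of stay) − 1 (PAID) = 28.

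*Actual size of the planned test.* Exact type I error of the chi-square/Fisher rule at 49 per arm, switching to Fisher when an expected count is below 5:

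| True event rate | Size |
|---|---|
| 3% | 0.16% |
| 4% | 0.43% |
| 5% | 0.83% |
| 10% | 3.9% |
| 15% | 5.3% |
| 70% | 4.9% |

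Assumed mix for the 28: 3 mortality tests at 4%, 8 binary items at 3%, 5 at 10%, 5 at 15%, chemotherapy access at 70%, and 6 continuous tests at 5% size. Only the mortality rate has a basis in the documents (3–4%).

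- Expected false positives: 3(0.0043) + 8(0.0016) + 5(0.0393) + 5(0.0535) + 0.0490 + 6(0.05) ≈ 0.84.
- Independent: 1 − 0.9957³·0.9984⁸·0.9607⁵·0.9465⁵·0.951·0.95⁶ ≈ 0.58.
- Correlation between endpoints within a patient (assumed; simulated): about 53% at 0.3 and 48% at 0.5.

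**5. Mortality precision.** Assume 2/49 versus 2/49. The Wilson limits for each arm are 1.1% and 13.7% around 4.1%. Newcombe interval for the difference: ±√[(0.041 − 0.011)² + (0.137 − 0.041)²] ≈ ±0.10, that is, −10 to +10 percentage points.

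**The case against.** The strongest reply is that the documents do single out the primary endpoint. Only the primary objective is framed as a superiority question, most secondary objectives are worded descriptively by group, the sample size serves one comparison, and discontinuation refers to significance of the primary endpoint. All of that is correct. A reader might infer that the plan makes no distinction at all between primary and secondary, or that the primary alpha is spent on the secondary tests. Neither follows: there is one primary endpoint, and these comparisons do not touch its error rate. What stands is that the analysis section then applies the same significance rule to everything and leaves secondary claims unlimited.

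A second reply is that a 90% chance of a false positive is too high. That also stands. A reader might take 90% as the expected figure, or suppose that rare complications are the main source of false findings. The documents support neither. The earlier series predicts real differences in several endpoints, complications overlap clinically, and the planned Fisher test makes rare events contribute almost nothing. With strong correlation (0.7) across all 44 tests the figure falls to 39%.

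Third, the plan does report summaries per arm, so it is not a bare verdict. The gap is narrower: no between-arm difference with an interval. Nor do the documents say that a non-significant mortality result will be reported as safety. The background wording only shows that such a reading is close at hand.

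**Conclusion.** The concern holds for secondary claims. About 44 comparisons are each tested at two-sided P < 0.05, any that pass may be called statistically significant, and nothing limits what may be concluded. A realistic chance of at least one false positive is roughly 50–60%, with about 0.8 expected. This rests on 28 plausible nulls, assumed event rates and correlation from none to moderate. The upper range is 60–90%, if all 44 nulls are true and tests have full size. Separately, a P value alone would conceal an uncertainty of about ±10 percentage points on mortality at an assumed 2 deaths per arm. The primary conclusion and its alpha are unaffected by this point.

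**What to change.** Replace the blanket significance rule in the Statistical Analysis section with:

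> Statistical significance is claimed for the primary endpoint only. Secondary endpoints are exploratory and are reported as between-arm differences with 95% confidence intervals, without a significance label.

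Every endpoint stays, and no further patients or data are needed. The cost is that fewer secondary results can be called significant. If the sponsor wants a formal secondary claim, it can name two or three key secondary endpoints in advance and test them in fixed order after a significant primary result. That is the sponsor's choice and not part of the required change. The wording should be settled before results by arm are known, because a limit on claims set afterwards is less credible.

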- Respiratory distress (defined as the need for mechanic ventilation after surgery)
- Urinary tract infection
- Neurological morbidity (cerebrovascular accidents, hemorrhage)
- Re-operation
- Re-admission within 30, 60 and 90 days

For PA Group additional secondary endpoints are:

- Incidence and severity of POPF ²⁸
- Incidence of biochemical leak ²⁸
- Overall average complication burden for POPF
- Incidence of postoperative pancreatitis ²⁹

SAMPLE SIZE CALCULATION

A recent metanalysis by Schuh et al. reported a POPF rate around 23% in stage D patients (main pancreatic duct diameter ≤ 3 mm, soft pancreas) but no data were available regarding major morbidity¹². Patients that will be considered eligible for the present trial will have further features increasing their risk of POPF and

related major morbidity, compared to stage D patients. Based on the current literature and on a recent retrospective study by the Verona group, considering only a cohort of patients with extremely high FRS (FRS 9-10), the rate of major morbidity can be estimated around 55% after PD and 19% after TP.¹¹

The original risk score proposed in this trial is extrapolated based on previous literature and expert opinions. For this reason, there are no data directly available for estimation of major morbidity in this rare subset of patients, for which we estimate a rate of Clavien-Dindo ≥ 3 of around 40%.

Considering a 1:1 allocation between the groups, a sample size of 49 patients per group would allow a two-sided, two-sample test for binomial proportions to detect a difference in Clavien-Dindo ≥ 3 of 25% (40% vs 15%) with 80% power ($1-\beta$) and an error α of 0,05. The study has a group sequential design allowing for interim analyses at pre-specified timepoints with possible early stopping for efficacy or futility in case of an overwhelming large or small effect, respectively. Considering that extremely high-risk cases represent around 7% of the total amount of PDs performed and that the fistula risk can only be assessed intraoperatively, we expect to approach preoperatively around 1300 patients.

STATISTICAL ANALYSIS

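### Interim stopping has no stated boundary, and the only written trigger, significance at P < 0.05, does not hold the 5% error rate

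*Combined protocol and SAP*

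**What the plan says.** Three sections of the combined protocol and SAP bear on this point.

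- **Sample Size Calculation.** The size is set by a conventional calculation: "a sample size of 49 patients per group would allow a two-sided, two-sample test for binomial proportions", for 40% versus 15% major morbidity, 80% power "and an error α of 0,05". The next sentence calls the design group sequential, with "interim analyses at pre-specified timepoints with possible early stopping for efficacy or futility in case of an overwhelming large or small effect". It gives no number or timing of looks, no efficacy or futility boundary, and no alpha-spending method. No other section supplies them.
- **Statistical Analysis.** One threshold serves all tests: "P values < 0.05 will be considered statistically significant". For binary endpoints the test rule is: "Categorical variables will be analyzed by Chi-square or Fisher's exact test in case of expected small frequencies". How small is not defined.
- **Duration and End of the Study.** "The study will be discontinued in case of reaching the statistical significance of the primary endpoint". The same section adds that "Long term analysis of QoL and pancreatic insufficiency will require additional 24 month of follow-up".

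**The concern.** The first section suggests that only a very large effect would stop the trial, but puts no number on it. The other two give a trigger that can be applied directly: P < 0.05 on the primary endpoint. A team following the document would test each interim look at the full 5%, and repeated testing at that level raises the overall error above 5%.

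Two things are at stake. One direction of the error is a false claim that total pancreatectomy reduces major morbidity. The sponsor's own retrospective series, described before the Aim of the Study, found insulin-dependent diabetes in every patient after that operation. Also, a trial stopped on a marginal early result overstates the benefit. Neither can be repaired credibly once interim data have been seen.

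**Working it through.** **Inputs.** From Sample Size Calculation: rates 0.40 and 0.15, 1:1 allocation, two-sided α = 0.05, power 80%, 49 per group. From Statistical Analysis: two-tailed tests, chi-square or Fisher's exact, P < 0.05. The number and timing of looks are not in the document and are assumed below.

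**1. The plan's own figure.** Pooled-variance formula, with p̄ = (0.40 + 0.15)/2 = 0.275:

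n = [1.960·√(2·0.275·0.725) + 0.842·√(0.40·0.60 + 0.15·0.85)]² / 0.25²
= [1.2377 + 0.5102]² / 0.0625 = 48.9, rounded up to 49 per group.

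The stated 49 is reproduced. It is a single-analysis size with no allowance for interim looks.

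**2. Type I error if every look uses P < 0.05.** Under a normal approximation with equally spaced looks, the overall two-sided error is 5.0%, 8.3%, 10.7%, 12.6% and 14.2% for 1 to 5 looks. Because the data are binary and the samples small, the error was also computed by exact binomial enumeration: 49 per arm, common event rates 0.15, 0.20, 0.25, 0.275, 0.30, 0.35 and 0.40. Two readings of the test rule were used: chi-square throughout, and Fisher's test whenever an expected count is below 5. Ranges run over the seven rates.

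| Looks (patients per arm) | Chi-square throughout | Fisher if an expected count < 5 |
|---|---|---|
| 49 only | 4.8–5.5% | 4.8–5.3% |
| 25, 49 | 8.5–9.1% | 7.0–9.1% |
| 16, 33, 49 | 11.0–11.6% | 7.8–11.0% |
| 10, 20, 29, 39, 49 | 13.0–13.5% | 9.1–11.9% |

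Counting only false claims in favour of total pancreatectomy, two looks give 3.5–4.6% against 2.4–2.8% for a single look.

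**3. What would stop the trial.** Take 9/25 versus 3/25 events at a half-way look. The pooled rate is 12/50 = 0.24 and the smallest expected count is 25 × 0.24 = 6, so chi-square applies under the usual cut-off of 5.

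z = 0.24 / √(0.24·0.76·2/25) = 0.24 / 0.1208 = 1.987, p = 0.047.

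A 24-point difference, below the 25 points the trial was sized for, meets the written trigger. It is hard to call that overwhelming.

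**4. Early stopping if the design rates are true.** With 40% versus 15% and looks at 25 and 49 per arm, 53% of trials stop at the first look under either reading of the test rule. The mean observed difference in those trials is 34 points, against a true 25.

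**5. A boundary that holds alpha.** One interim look at 25 per arm with O'Brien-Fleming-type spending: |z| ≥ 2.963 (p about 0.003) at the interim and |z| ≥ 1.969 (p about 0.049) at the end. Enumerated with chi-square over the same seven rates, type I error is 4.7–5.1%. Under 40% versus 15%, power is 80.9% and the chance of stopping early is 14%.

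**The case against.** The strongest reply is that the document never says outright that interim looks are tested at 0.05. A group sequential design with looks fixed in advance and stopping only for an overwhelming effect fits a strict boundary. The P < 0.05 sentence is a general one, and reaching significance could mean crossing that boundary. A stricter rule may well have been intended. But none is written, and the sentence that ends the study asks only for significance, which has one definition. The intention cannot be applied; the written rule can.

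A second reply is that Fisher's exact test is conservative. Used at every look, it gives 3.7–5.1% for two looks and 4.4–6.0% for three. The 9/25 versus 3/25 example would then not be significant (Fisher p = 0.095; continuity-corrected chi-square p = 0.098), and early stopping under 40% versus 15% would fall from 53% to 38%. The arithmetic is right, but it is not the plan's rule: Fisher is reserved for small expected frequencies. At 25 per arm and the 27.5% pooled design rate the smallest expected count is 25 × 0.275 = 6.9.

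Three smaller points stand as limits. The size depends on an unstated number of looks, and the five-look case is only an upper illustration. With 98 patients enrolled over 22 months and 3 months of follow-up, about 98/22 × 3 ≈ 13 patients would be awaiting outcome at any look, so the 34 points is the interim estimate and not necessarily the final reported one. The 81% power assumes no futility stops.

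**Conclusion.** The concern holds, and it should be corrected before any interim analysis. The sections conflict, and the one stopping rule that can be applied as written does not keep the stated two-sided 5%. With a single half-way look, the least any interim design can have, the error is 7.0–9.1% across common event rates of 15–40%, and it rises with more looks. This assumes 49 per arm, looks at the sample sizes shown, chi-square with or without Fisher's test below an expected count of 5, and P < 0.05 at each look. The sample size of 49 is correct for a single analysis; the fault lies in the stopping rule.

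**What to change.** Reconcile Sample Size Calculation with Duration and End of the Study. State the number of looks, their timing in patients with a complete primary outcome, the efficacy and futility boundaries, the alpha-spending method and the final-look threshold. Replace the significance trigger with crossing the stated efficacy boundary.

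One workable choice among several is the single interim look in step 5 of the working, with futility declared non-binding so that alpha does not depend on it. If the team expects to act on futility, power should be recalculated with that boundary included.

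The protocol should also make clear that an efficacy stop ends enrolment only, and that the planned 24-month follow-up of randomised patients continues.

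The cost is mainly wording. With the example boundary, 49 per group still gives about 81% power. The price is a slightly stricter final threshold and fewer early stops, about 14% instead of 53% under 40% versus 15%. Other boundaries cost more: Pocock-type limits at 49 per group give power of about 77%, 74% and 71–72% for two, three and five looks, so they would need more patients (about 55 per group for two looks and 58 for three).
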